- There will be reduced CT in the visual cortex in the low vision groups compared to matched controls at baseline
- Reading rehabilitation results in increased CT in the low vision groups, but not in the control group after 12 months.

Ethics Approval has been obtained through the *Comité d'éthique de la recherche* of the *Centre de recherche interdisciplinaire en readaptation du Montreal metropolitan (CRIR#1284-1217)* which is responsible for research protocols involving recruitment from the clinical partners (local sensory rehabilitation centres) within this study: the *CRIR/Centre de réadaptation MAB-Mackay du CIUSSS du Centre-Ouest-de-l'Île-de-Montréal*, and the *CRIR/Institut Nazareth et Louis-Braille du CISSS de la Montérégie-Centre* (see attached letters of support). Additional approvals and modifications (MRI component) will be obtained through the university affiliations of the team members.

Study Design: We will employ a quasi-experimental approach (non-randomized, pre-post intervention study)⁶³, an approach frequently used during the evaluation of health interventions⁶⁴. Specifically, a 3x3 design (3 groups x 3 time points) will allow us to examine whether cognitive performance will change before and after 6 and 12 months of a low vision reading intervention, when comparing LV and dual sensory impaired (DSI) patients to age-matched controls with age-normal vision and hearing⁶⁵. Participants will be audio-recorded throughout several of the tasks to ensure the highest level of precision when inputting and analysing data, and to help reduce the overall testing time. All aspects of the study design and data analysis will be submitted as a stage 1 pre-registered report.

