Participants: We will recruit 150 new clients (65+ years of age) referred for low vision rehabilitation to either of the two vision rehabilitation centres in Montreal (Lethbridge-Layton-Mackay and INLB, see partner letters of support), and 50 age-matched (by decade) older adults without visual impairment (to be recruited from spouses or family members of participants, as well as through open advertisement through media and senior groups). In addition, we have access to the *Banque des participants* of the *Centre de recherche institut universitaire de geriatrie de Montreal (CRIUGM; n > 1000)*. Within this database, it will be possible to match our control participants on variables such as age, gender, education, and other potential variables of interest such as MoCA score). Client-participants are

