required to have a diagnosis of AMD (any type), not currently be undergoing any medical treatment for their AMD (e.g., anti-VEGF injections) and must potentially benefit from a magnification intervention for the purpose of improving their ability to read. This reading intervention requirement (see description in data collection section below) will likely result in a large number of eligible participants as reading has been reported to be the number 1 complaint of individuals seeking vision rehabilitation⁶⁶. Participants need to be able to communicate in either English or French, and have a visual acuity in the better eye of 20/60 or less with best standard refraction, according to the admission criteria for eligibility for rehabilitation services in Quebec⁶⁷. DSI participants are eligible with an additional unaided pure-tone average (PTA) hearing loss across 4 frequencies (0.5, 1, 2 and 4 kHz) between 26 dB and 70 dB⁶⁸. Those with a PTA \geq 70 dB HL in their better ear are likely to have severe problems in speech communication, and will be excluded from recruitment. Based on past experience, because we will recruit participants over the phone, those with more severe degrees of hearing impairment would unlikely be recruited for the project. Progress of our pilot study^{57,58} indicates that we will be able to recruit at least 3 AMD participants per week, making the recruitment goal feasible within 18 months. Given the familiarity of the team members of working with this population, it is our experience that recruitment is most successful when we offer the choice of coming to the lab space at either rehab centre or to be visited in their home for data collection (except for the MRI sub-study, whose participants will be randomly recruited among study participants). Therefore, informed written consent will be obtained and data will be collected either in the home or the lab at the first in-person meeting, and the procedures are developed accordingly to be easily portable.

Measures: The study includes outcomes measures of vision (e.g., reading), cognition (e.g., memory) and cortical architecture (MRI sub-study), as well as potential descriptors, clinical data and co-variants (e.g., hearing, demographics, depression etc.)

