Clinical Variables: As part of any low vision exam, the eye care professionals within each of the rehabilitation centres record key variables in the patients' charts that will be available for extraction by the research team as part of their study consent. They include, but are not limited to: diagnoses (ocular and otherwise), monocular and binocular visual acuity (distance and near), contrast sensitivity, visual field diameter, type and duration of rehabilitation services provided (e.g., computer rehab, orientation & mobility services), type of assistive devices that were prescribed and provided (please note that these devices are free loans for life through Quebec Health Insurance/RAMQ; therefore, income is not a barrier to device use). The file contains information about the type and intensity of vision rehabilitation strategies that were implemented and trained (e.g., provision of improved lighting, strategies to read while placing materials on reading stands at the appropriate distance). In addition, the file contains basic demographic information (e.g., gender, age, living situation). These clinical variables will be available to the research team for the purpose of comparison, as well as statistical control and analysis.

MRI Acquisition – Subsample of 45 Participants (15 VI, 15 DSI, 15 control)

Imaging data will be acquired using a 3T Siemens Prisma fit MR scanner (Siemens, Erlangen, Germany) at the *Unité de neuroimagerie fonctionnelle of the Institut universitaire de gériatrie de Montréal*. High-resolution T1-weighted images will be acquired using a magnetization-prepared rapid acquisition with gradient-echo (MPRAGE) sequence, with the following parameters: TR=2.4 s,

TE=2.33 ms, TI=979 ms, flip angle=9 degrees, FOV=230x230, voxel size: 0.8 mm x 0.8 mm x 0.8 mm. Additional FLAIR, resting-state and DTI sequences will also be included as exploratory measures. Total acquisition time will last < 30 minutes plus 15 min instruction and preparation.

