- 2) If no such clear division occurs but participants naturally distribute along a continuum of reading effort and reading behaviour variables, we can simply use the reading measure(s) as co-variables to test whether any/all of the reading effort measures emerge as significant co-variables, and examine whether cognitive scores improved over time across our three groups, after removing the effect of reading rehabilitation success.
- 3) Finally, we will use **latent factor analysis** to explore whether specific clusters of variables are specifically associated with improvements in cognitive functioning and/or improved reading ability. This analysis will be led by [name], together with [name] and [name].

Statistical Analysis - Cortical thickness:

Regression analyses of visual impairment on cortical thickness will be investigated at each vertex of the cortical surface using general linear modeling. Cortical thickness will be modeled as a function of group by controlling for the effects of age, gender, and education. Resulting clusters will be considered significant at $p < 0.05$ using a Monte-Carlo simulation approach. Similar analyses will be performed for cortical volume and cortical surface area, with the addition of total intracranial volume as a nuisance factor¹¹². In addition, a region-of-interest approach will be used to extract the CT values in specific regions of interest using the Destrieux cortical atlas¹¹³ in FreeSurfer. More specifically, we will compare across groups CT values extracted within specific regions of the visual cortex including the

[name]

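### The matched controls of the cortical-thickness hypothesis are not secured in the 15 MRI controls, and the region-of-interest comparison names no covariates

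*Combined protocol and SAP*

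**What the plan says.** - **Hypotheses:** "There will be reduced CT in the visual cortex in the low vision groups compared to matched controls at baseline".
- **Participants, parent sample:** 150 rehabilitation clients and "50 age-matched (by decade) older adults without visual impairment". Controls come from spouses or family members, open advertisement and a participant bank. For the bank the plan adds that "it will be possible to match our control participants on variables such as age, gender, education", along with other variables such as the MoCA score. This is an option, not a rule.
- **Participants, imaging:** home or lab testing is offered "except for the MRI sub-study, whose participants will be randomly recruited among study participants". The MRI Acquisition heading sets 15 visually impaired (VI), 15 dual-impaired (DSI) and 15 control participants. No matching or stratifying factor is given for the draw beyond these quotas.
- **Statistical Analysis – Cortical thickness:** for the whole-surface model, "Cortical thickness will be modeled as a function of group by controlling for the effects of age, gender, and education". The region-of-interest analysis is then introduced as an addition: "we will compare across groups CT values extracted within specific regions of the visual cortex including the" listed occipital regions. No covariates are named there or in the text on change over time.
- **Sex, Gender, Equity, Diversity & Inclusion:** gender is to be considered as a control in all analyses, and more women than men are expected to take part.

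**The concern.** The hypothesis names a property, matching, that the selection rule for the MRI sub-study does not secure. A match by decade across 50 controls need not survive in 15 of them. Gender has no committed match at any level, and the recruitment routes may push it apart: if most clients are women, spouses recruited as controls will tend to be men.

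Two things are at stake. Where age, gender and education are in the model, imbalance widens the confidence interval of a comparison that is already small. Where they are not, imbalance moves the estimated group difference in cortical thickness. The plan commits to a stage 1 pre-registered report, so the selection rule and the covariates should be fixed in writing beforehand.

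**Working it through.** **The plan's own figures.** The documents give no power, effect size or precision for the 45-person sub-study. The main-study N of 141 reproduces (3 x 3 interaction, f = 0.15, alpha 0.05; power 0.952, assuming correlation 0.5 and sphericity), but it does not bear on the MRI comparison.

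**Inputs.** From the documents: groups of 15, 15 and 15; covariates age, gender and education; parent groups of 150 and 50. Assumed: age SD 7 years, the gender mixes shown below, normal age and education, a two-sided 0.05 test, no MRI dropout.

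**Step 1. Size of a chance age gap, 30 low vision v 15 controls.** With equal means in the source groups, the SD of the gap is 7 x sqrt(1/30 + 1/15) = 2.2 years. Allowing for drawing 30 of 150 and 15 of 50, it is 7 x sqrt(0.805/30 + 0.714/15) = 1.9 years, where 0.805 = 120/149 and 0.714 = 35/49. A gap over 3 years then occurs in about 12% of draws (3/1.9 is about 1.57 SD, two-sided).

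**Step 2. Precision in the adjusted model, source groups alike.** With q = 3 chance-imbalanced covariates and 45 - 3 = 42 degrees of freedom before adjustment, the expected variance inflation is 1 + q/(42 - q - 1) = 1 + 3/38 = 1.079. Simulation (20,000 draws, 65% women in every group) gives 1.08 for the 30 v 15 contrast. Matching on age band and gender lowers it to about 1.03. Most of the remainder is education, which is not matched: 1 + 1/40 = 1.025. The recovery is 4 to 5 points of variance. In standard error, sqrt(1.031/1.078) = 0.978, about 2% shorter.

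**Step 3. Precision if gender mix differs (assumed 70% women among patients, 40% among controls).** The within-group sum of squares for gender is about 28 x 0.21 + 14 x 0.24 = 9.24. The systematic gap of 0.30 adds 0.30^2 / (9.24 x (1/30 + 1/15)) = 0.09/0.924 = 0.097 to the inflation. With the chance part, 1 + 0.079 + 0.097 = 1.18. Simulation, which averages over unfavourable draws as well, gives 1.20, against 1.03 with matching: sqrt(1.03/1.20) = 0.926, a standard error about 7% shorter.

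**Step 4. What this means for detectable differences.** For 30 v 15 at 80% power with 39 degrees of freedom, before any correction for regions or vertices: 0.91 SD with perfect balance, 0.94 SD at inflation 1.079, and just under 1.00 SD at inflation 1.20.

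**Step 5. The region-of-interest comparison, if unadjusted.** Shift in SD units = correlation of age with thickness x age gap / age SD. With an assumed correlation of 0.2 to 0.5, a 3-year gap shifts the contrast by 0.2 x 3/7 = 0.09 to 0.5 x 3/7 = 0.21 SD.

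**The case against.** The case against has several good parts.

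- A random draw from a control group matched by decade keeps that match on average, and the 15/15/15 quotas already stratify by sensory group. This stands: the controls should not be called unmatched, only not ensured to be matched.
- The whole-surface model adjusts for all three covariates. This stands, and removes the bias argument there apart from its usual linearity assumption.
- The 8% is the total cost of imbalance, not what matching returns. This also stands; if the source groups are alike the return is about 2% of the standard error, and the sub-study's size matters far more.
- The region-of-interest analysis follows directly on the adjusted model, and gender is promised as a control throughout. This stands for gender. Age and education are not named for these comparisons.
- The 12-month outcome is within-person percentage change, so baseline imbalance matters less there. Agreed; the point concerns the baseline hypothesis.
- Equal numbers of VI, DSI and control participants per stratum would be hard to draw. Patients are enrolled on a rolling basis and need a scan before rehabilitation starts, within about 3 months. This stands against a three-way stratified draw, but not against choosing controls, who have no rehabilitation deadline.

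A reader might also infer that VI and DSI participants should be matched to each other. The documents do not support that: the hypothesis calls only the controls matched, against the low-vision groups, and no age difference between VI and DSI is given from which to size a cost.

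**Conclusion.** The point holds in limited form. Matching to the low-vision groups is stated in the hypothesis, but in the MRI subset it is secured only in expectation for decade of age, and not by rule for gender.

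In the whole-surface model the consequence is lost precision, not invalidity: about 8% of variance if the source groups are alike, of which matching recovers 4 to 5 points. The gain is larger if gender mix differs: about 20% v 3% inflation at the assumed 70% v 40% women. The documents make such a difference plausible but give no figures for it, nor for the age SD.

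For the region-of-interest comparison the gap is one of wording with a possible consequence for validity: if age and education are left out, an imbalance moves the estimate. The documents do not show that they will be left out, only that they are not named. A reader should not conclude that the imaging comparison is biased as planned. This is a small improvement worth making.

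**What to change.** 1. Keep the random selection of VI and DSI participants for MRI. Select the 15 MRI controls by frequency matching on age band (for example 65–74, 75–84, 85 and over) and gender to the 30 scanned low-vision participants, and say that this is what matched means in the hypothesis.
2. State that the region-of-interest group comparisons use the same age, gender and education covariates as the whole-surface model.

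The cost is two sentences and a sampling list, with no extra participants or scans. The 50 controls should usually suffice: even at an assumed 40% women there are 0.40 x 50 = 20 women for the 0.70 x 15 = 10.5 places needed, before refusals or MRI contraindications. The downside is scheduling. Control scans must follow, or run in step with, patient scans. Rare strata may take slightly longer to fill, and the last 12-month control scans would move back accordingly.

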Cognitive Outcome Measures: We will investigate the potential effect of reading rehabilitation on three relevant areas of cognitive function. The first will be episodic learning and memory, assessed using the Rey Auditory Verbal Learning Test (RAVLT)⁶⁹. Second, we will assess two aspects of auditory working memory: a) general auditory working memory and will be assessed using the WAIS-IV Letter Number Sequencing task⁷⁰ and b) an auditory listening span test, which will be a variant of the reading span task originally developed by Daneman and Carpenter⁷¹ (a task highly associated with reading skill). The third domain is processing speed, and will be assessed using a computerized audio-visual choice reaction time task. Lastly, we will be assessing cognitive impairment using the adapted version of the Montreal Cognitive Assessment (MoCA)^{59,72} for persons with visual impairment, should their visual impairment be too severe to administer the visual items. This measure will provide additional information regarding the participants' cognitive abilities, and help to identify possible cognitive impairment. These measures were chosen because they cover a wide range of cognitive functions, they are all **administered in the auditory domain** and thus will not be affected by a visual impairment, and have good psychometric properties. In other words, should performance on these cognitive measures improve following the vision rehabilitation program, the improvement will be attributable to the benefit of increased visual function on cognitive stimulation as opposed to merely being due to improved perception of the stimuli involved in the tests. Their administration can be **adjusted to make instructions audible** for persons with concurrent hearing loss. Moreover, they assess cognitive domains that have been shown to predict everyday function in older adults: episodic learning and memory⁷³, processing speed⁷⁴, and working memory⁷⁵. In addition, we have aimed to harmonize as many of our cognitive measures as possible with those utilized in the Canadian Longitudinal Study on Aging, in order to increase the possibilities to compare our findings to that larger data set for 30,000 Canadians for whom baseline and first follow-up data are available⁷⁶.

Reading Outcome Measures:

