To subjectively assess reading effort, we will administer a reading habit questionnaire, a measure developed specifically to evaluate the extent and frequency to which an individual engages in reading activities during their activities of daily living, including reading for entertainment or education. This measure has previously been employed by our team³⁹ and includes questions on language background (e.g., mother tongue, language proficiency), assessed self-reported proficiency in reading (1=no ability, 5=fluent ability), and reading habits before and after onset of low vision (e.g., frequency, enjoyment, type of reading). In addition, participants will be asked to read English or French paragraphs from the

International Reading Speed Test (IReST)⁷⁷. It includes reading comprehension questions that have previously been developed and used in our lab in the context of a low vision reading evaluation using the iPad as a magnification device³⁹. They will also read the English or French version of the MNRead chart⁷⁸, a clinical assessment chart that allows for the measurement of reading acuity (smallest print read), reading speed (in words per minute), critical print size (smallest print at which reading speed is still optimal), and the Reading Accessibility Index⁷⁹, which considers reading ability over a range of print sizes. Finally, we administer a primed lexical decision task where the participant first reads a sentence (prime) and then decides on a word (target) as quickly and as accurately as possible. This task evaluates reading speed, vocabulary comprehension and ability to judge content congruency^{80,81}.

Measures of Participant Characteristics

Depression, Anxiety, Stress: Not surprisingly, the onset of age-related vision loss due to AMD is often accompanied with a multitude of emotional responses that can potentially interfere with the success of low vision rehabilitation. Therefore, the Depression, Anxiety and Stress Scale⁸² will be included in the protocol in order to identify individuals whose rehabilitation outcomes might be influenced by their psychological state. This 21-item questionnaire shows exquisite psychometric properties and has been validated in both English and French⁸³.

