Hearing Assessment: Given that the cognitive assessment is designed in such a way that vision is not required for the administration of the testing materials, and given that the influence of **hearing** loss has been associated with the measurement of cognition^{e.g., 84} and has been identified as a risk factor for cognitive impairment²⁴, hearing ability will be assessed as part of the protocol. In order to be able to consider hearing ability and listening effort during the cognitive assessment²⁹, participants will complete a pure-tone audiogram with a portable audiometer (Maico MA41 from GénieAudio), using Radioear DD45 earphones, to establish a mean unaided decibel hearing loss (dB HL) threshold across 0.5, 1, 2, and 4 kHz in each ear. We will document the ambient sound levels during testing, using the Decibel X app by SkyPaw Co. Ltd., because testing may be conducted in participants' homes. Ambient noise levels can then be used to statistically control for potential noise effects on hearing thresholds. For individuals who experience difficulties in hearing the experimental protocol instructions, we will have a Williams Sound Pocketalker (<https://www.williamsound.com/pocketalker>) on site in order to provide personalized amplification. In addition to pure-tone audiometric thresholds, speech-in-noise thresholds will be measured using the Canadian Digit Triplet Test in either English or French⁸⁵. Participants will complete the Hearing Handicap Inventory for the Elderly (HHIE) questionnaire and three individual questions about hearing ability which assesses their perception of difficulties with activities of daily living that require hearing⁸⁶. These hearing assessments are the same as those that have been used or are planned for the Canadian Longitudinal Study on Aging (CLSA)⁸⁷, thereby allowing us to cross-reference and compare data from both studies and optimize our ability to place our intervention findings in a larger Canadian context.

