Sample Size: Effect sizes in vision rehabilitation in the past have ranged from approximately Cohen's $d = .20$ to 2.5 ³⁸. Since there are no existing effect size estimates for cognitive ability in the context of low vision rehabilitation, we are applying these values as a guide line: Using an average value of $d = 1.0$, and converting this value into variance accounted for ($r^2 = .20$ ¹⁰⁵), we can estimate a required sample size. Using a 3x3 (group x time point) within-between design for Analysis of Variance, power analysis using gPower¹⁰⁶ indicates that a sample size of $n = 141$ allows us to detect small effect sizes of .15 or greater, with an alpha of 0.05 and a desired power of .95. We expected an attrition rate of around 10% at each time point, given our previous research with older visually impaired adults^{107,108}. Therefore, a sample of $n = 200$ (to yield 150 patients, 50 controls) should be sufficient for our protocol. This goal is feasible given an average of 3000 new referrals to rehabilitation in Montreal per year.

Data Collection

Time 1 – Pre-Reading Rehabilitation: Participants will complete the questionnaires, hearing, reading and cognitive assessment components between their initial global intake exam and their first rehabilitation appointment. This period can span anywhere around 3 months, depending on waiting lists, and we will track whether any substantial changes in health occurred during this period that could influence eligibility or data collection.

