Time 2 – 6-Months and Time 3 – 12-Months Follow-Up: Six and 12 months after the initial rehabilitation appointment, the research assistant will meet with each participant (at home or in the lab, according to their preference) in order to repeat the experimental protocol, and all reading, cognitive and hearing measures will be administered each time. Throughout the period of the protocol, data from the rehabilitation chart will be extracted as it becomes available, with the final data collection concluding after the 12-month follow-up.

Statistical Analysis – Functional measures: To analyze these data, we will examine change in cognitive test scores from baseline over time using mixed-effects regression models, adjusting for level of vision and hearing impairment as fixed or random effects, and compare across sensory group (VI/DSI/Control). The analyses will include consideration of potential moderators or confounders (i.e., gender, age, education). In addition, we will calculate effect sizes, confidence intervals and Bayes Factors for main effects, interactions, and all post-hoc analysis.

When reflecting on the question of a control group we further consulted with the rehabilitation centres and discussed recruitment approaches and limitations; however, for practical and ethical reasons we are not able to withhold rehabilitation services from a possible comparison group, and waiting times are too varied across the centers and seasons of the year to allow for a waiting-list control group. As a result, we are proposing a quasi-experimental repeated-measures design with the intent to let the participants act as their own comparison across time points.

In addition, the data allow us to follow potential **exploratory avenues of analysis:**

- 1) If the recruited participants naturally divide into individuals whose reading effort was reduced and their reading activity has increased, versus those where we do not observe a change in reading behaviour, we can compare these two groups directly (e.g., while still considering their hearing status, or their gender)

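### The claim that all cognitive tests are auditory does not cover the audio-visual reaction-time task, the only processing-speed measure, and by inference may not cover the MoCA

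*Combined protocol and SAP*

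**What the plan says.** The section Cognitive Outcome Measures names five measures: the RAVLT, Letter Number Sequencing, a listening span test, a choice reaction time task and the MoCA. It then says that all of them are given in the auditory domain and are therefore not affected by visual impairment. From this it concludes that a gain after rehabilitation would be attributable to cognitive stimulation through better visual function, "as opposed to merely being due to improved perception of the stimuli involved in the tests".

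Two descriptions in the same paragraph sit badly with that statement. Processing speed "will be assessed using a computerized audio-visual choice reaction time task". The adapted MoCA is offered to persons with visual impairment, "should their visual impairment be too severe to administer the visual items".

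The section Hearing Assessment repeats the premise, saying that the cognitive assessment is designed so that "vision is not required for the administration of the testing materials". It makes no claim about how gains are to be attributed.

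On timing, Time 1 places the "cognitive assessment components between their initial global intake exam and their first rehabilitation appointment". The section on the low vision intervention then describes refraction, glasses, optical and electronic devices and, for some participants, lighting advice. At 6 and 12 months, "all reading, cognitive and hearing measures will be administered each time". The mixed models compare change in cognitive scores across groups, "adjusting for level of vision and hearing impairment as fixed or random effects".

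**The concern.** The intervention changes what participants can see. If a cognitive test has a visual part, a better score after rehabilitation could come from seeing the test better and not from better cognition. The protocol recognises this alternative and sets it aside by saying that all tests are auditory. For the reaction-time task, the protocol's own description does not support that.

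What is at stake is how a change in processing speed is interpreted. As written, a reaction-time gain would be read as cognitive benefit although changed perception of the stimuli has not been excluded. The same could apply to the MoCA if its visual items are given to some participants, or at some visits and not others.

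**Working it through.** No figure in the plan bears on this point, so the check sets the statements side by side. All descriptions come from Cognitive Outcome Measures.

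| Measure | Domain | Modality as described | Covered by the auditory argument? |
|---|---|---|---|
| RAVLT | Episodic learning and memory | Auditory by name | Yes |
| Letter Number Sequencing | Working memory | Auditory | Yes |
| Listening span | Working memory | Auditory | Yes |
| Choice reaction time | Processing speed | Audio-visual | No, by its own description |
| MoCA | Outside the three domains; additional information | Adapted version tied to severity of impairment | Uncertain; depends on the version given |

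**Count.** Measures not covered on the text alone: 1 of 5. Domains not covered: 1 of 3, and that domain has no other test. Measures clearly covered: 3 of 5, spanning 2 of 3 domains. If the inference about the MoCA is right, the uncovered count is 1 + 1 = 2 of 5.

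**The MoCA inference.** The adapted version is described as conditional on impairment too severe for the visual items. The natural reading is that other participants receive those items. Controls have no visual impairment and so do not meet that condition. No section fixes one version for all participants, or for one participant across visits.

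**Can vision at testing change between visits?** Yes. Baseline cognitive testing precedes the first rehabilitation appointment, glasses and devices come afterwards, and the tests are repeated at 6 and 12 months. No section says which correction, device or lighting applies during cognitive testing. Vision could also worsen over the year, so an effect could go in either direction.

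**Do the planned comparisons remove it?**
- Controls are recruited without visual impairment, and rehabilitation is described only for the centres' clients. Controls would therefore not show a gain from better perception of the test.
- The model adjusts for level of vision, but the plan does not say which measure this is or whether it is updated at each visit.
- Clinical Variables lists distance and near acuity, contrast sensitivity and visual field as available for statistical control. The exploratory analyses allow reading measures as co-variables. These are useful data, but neither section ties them to this question.

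**The case against.** The strongest reply is that the attribution sentence explains why the tests were chosen. It is not an analysis rule, and the statistical section contains none. That is correct. The sentence also says merely, so it rules out perception as the whole explanation and not as a part. Even that weaker exclusion rests on auditory administration, which the reaction-time task does not have by its own description.

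Second, the stimuli may be visible to everyone. The team reports adapting cognitive tests for low vision, and eligibility acuity is already taken with best standard refraction. This stands, and it is why no bias can be asserted. A reader might infer that reaction-time results will be biased, or that the cognitive findings as a whole are contaminated by vision. The documents support neither: the stimuli are not described, no size or direction of a visual effect is given, and three tests fit the auditory statement.

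Third, the MoCA may not be exposed. Every patient has an acuity of 20/60 or worse, and Hearing Assessment says that vision is not needed, so use of the adapted version for most or all patients is plausible. This also stands. A reader might treat two of the five measures as shown to be visual, but only the reaction-time task is established by the text.

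Fourth, the design and analysis are to go into a stage 1 pre-registered report, where the stimuli and the MoCA version could be specified. That makes the point easy to correct, but it does not make the present wording accurate.

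**Conclusion.** The concern holds for one measure and is possible for a second. The auditory-administration argument does not cover the reaction-time task: 1 of 5 named measures, and the whole of processing speed, 1 of 3 domains. For the MoCA it may fail, on the assumption that participants who can see the visual items are given them.

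The lead question concerns memory. The RAVLT, Letter Number Sequencing and listening span are not open to the test-perception explanation, so that question is not affected by this point. The finding is that the stated exclusion is unsupported for processing speed, not that bias is present. No numeric bound is possible, because the documents give nothing from which to derive one. The wording should be corrected before the plan is fixed in the pre-registered report.

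**What to change.** 1. In Cognitive Outcome Measures, limit the auditory-domain and attribution statements to the RAVLT, Letter Number Sequencing and listening span. Bring the premise in Hearing Assessment into line. Describe the reaction-time stimuli, and interpret reaction-time change as possibly vision-dependent unless that description shows otherwise.
2. For outcome analyses, score the MoCA at every visit on the items common to the standard and adapted versions, for every participant including controls. Keep the full score as descriptive. This assumes that item-level scores are kept and that such common items exist; the documents do not describe the adapted version's content.

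The cost is wording and one scoring rule. The downside is that comparability with full MoCA scores is lost for that outcome.

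Optionally, and only as exploratory work, reaction time could be adjusted for vision at each visit, using the acuity data under Clinical Variables where charted, or the reading measures that the exploratory analyses already allow as co-variables. Reading is what the intervention targets, so this may over-adjust, and it cannot by itself separate test perception from a real effect.
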